7.4.1.4 Procedure for Reporting Serious Adverse Events and Non-serious Adverse Drug Reactions

In the event of any new SAE or new non-serious ADR occurring during the reporting period, the Investigator must immediately (within a maximum 24 HOURS after becoming aware of the event) report to Merck Serono Global Drug Safety Department by telephone, by fax or by emails.

Names, addresses, telephone and fax numbers for AE reporting as follows:

Merck Serono Global Drug Safety Department

Address: Merck KGaA, [name];

Email: [contact]

[contact];

Telephone: PPD [REDACTED]

When an SAE or its follow-up information is reported by telephone, a written report must be sent immediately thereafter by fax or e-mail. Names, addresses, and telephone and fax numbers for SAE reporting will be included in the trial-specific SAE Report Form.

Reporting procedures and timelines are the same for any new information on a previously reported SAE (= follow-up).

All written reports should be transmitted with the Adverse Event Safety Report Form (Clinical Trials), which must be completed by the Investigator following specific completion instructions.

The AE section of the CRF must be completed, and a copy of the information must be transmitted along with the Adverse Event Safety Report Form (Clinical Trials). Relevant pages from the CRF may be provided in parallel (for example, medical history, concomitant drugs). Additional documents may be provided by the Investigator, if available (for example, laboratory results, hospital report, autopsy report). In all cases, the information provided on the SAE Report Form must be consistent with the data about the event recorded in the CRF.

The Investigator/reporter must respond to any request for follow-up information (for example, additional information, outcome, final evaluation, other records where needed) or to any question the Sponsor may have on the AE within the same timelines as those noted above for initial reports. This is necessary to ensure that the Sponsor promptly assesses the event and, where applicable, meets the strict regulatory timelines with expedited safety reporting.

Requests for follow-up will usually be made via the responsible Monitor. Although in exceptional circumstances the Global Drug Safety department may contact the Investigator directly for further information or to discuss the event.

7.4.1.5 Safety Reporting to Health Authorities, Independent Ethics Committees and Investigators

The Sponsor will send appropriate safety notifications to Health Authorities in accordance with applicable laws and regulations.

The Investigator must comply with any applicable site-specific requirements related to the reporting of SAEs (particularly deaths) involving trial subjects to the IEC/IRB that approved the trial.

In accordance with the ICH GCP guidelines, the Sponsor will inform Investigator of “findings that could adversely affect the safety of subjects, impact the conduct of the trial or alter the IEC’s approval/favorable opinion to continue the trial.” In particular and in line with respective applicable regulations, the Sponsor will inform the Investigator of AEs that are both serious and unexpected and are considered to be related to the administered product (“suspected unexpected serious adverse reactions” or SUSARs). The Investigator should place copies of the safety reports

in the Investigator Site File. National regulations with regard to Safety Report notifications to Investigators will be taken into account.

When specifically required by regulations and guidelines, the Sponsor will provide appropriate Safety Reports directly to the concerned lead EC/IRB and will maintain records of these notifications. When direct reporting is not clearly defined by national or site-specific regulations, the Investigator will be responsible for promptly notifying the concerned IEC/IRB of any Safety Reports provided by the Sponsor and of filing copies of all related correspondence in the Investigator Site File.

7.4.1.6 Monitoring of Subjects with Adverse Events

AEs are recorded and assessed continuously throughout the trial (see Section **Error! Reference source not found.**) and are assessed for final outcome at the 30-Day Follow-up Safety Visit. All SAEs ongoing at the 30-Day Follow-up Safety Visit (note any other type or category of AE to be followed up) must be monitored and followed up by the Investigator until stabilization or until the outcome is known, unless the subject is documented as “lost to follow-up”. Reasonable attempts to obtain this information must be made and documented. It is also the responsibility of the Investigator to ensure that any necessary additional therapeutic measures and follow-up procedures are performed.

7.4.2 Pregnancy and In Utero Drug Exposure

Pregnancies are not considered per se to be adverse events. However, all pregnancies with an estimated conception date during the period defined in Section 7.4.1.3 must be recorded by convention in the AE page/section of the CRF. The same rule applies to pregnancies in female subjects and to pregnancies in female partners of male subjects. The Investigator must notify the Sponsor in an expedited manner of any pregnancy using the Pregnancy Report Form, which must be transmitted according to the same process as described for SAE reporting in Section 7.4.1.4.

Investigators must actively follow up, document and report on the outcome of all these pregnancies, even if the subjects are withdrawn from the trial.

The Investigator must notify the Sponsor of these outcomes using the Pregnancy Report Form, and if an abnormal outcome occurs, the SAE Report Form if the subject sustains an event and the Parent-Child/Fetus Adverse Event Report Form if the child/fetus sustains an event.

Any abnormal outcome must be reported in an expedited manner as described in Section 7.4.1.4, while normal outcomes must be reported within 45 days from delivery.

In the event of a pregnancy in a subject occurring during the course of the trial, the subject must be discontinued from trial medication immediately. The Sponsor must be notified without delay and the subject must be followed as mentioned above.

7.4.3 Clinical Laboratory Assessments

All clinical laboratory assessments have been detailed listed in Section 7.1 and Section 7.2.

7.4.4 Vital Signs, Physical Examinations, and Other Assessments

All vital signs, physical examinations, and other assessments have been detailed listed in Section 7.1 and Section 7.2.

7.5 Pharmacokinetics

Not applicable.

7.6 Biomarkers

Not applicable.

7.7 Other Assessments

Not Applicable.

8 Statistics

8.1 Sample Size

A single-arm, interventional, multi-center pilot study to evaluate the efficacy of different dose of oral Bisoprolol on heart rate reduction in Chinese Chronic Heart Failure (CHF) patients with New York Heart Association (NYHA) class II – IV.

Suppose the difference of Mean change from baseline follows normal distribution, and the following assumptions are made to determine the sample size:

- It is supposed that the mean change from baseline of heart rate is -3.8bpm at week 6 and -7.4bpm at week 14. The Standard Deviation is assumed to be 10bpm across time.
- Based on assumption above about treatment effect and up-titration status at different visit, assuming 236 subjects under 15% dropout rate, distance from mean to limit of the 95% confidence interval of the change from baseline of mean heart rate is 1.54 at week 6 and 2.12 at week 14. Due the limit evidence at week 26, there is no robust extrapolation.

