8.3 Endpoints

8.3.1 Primary Endpoints

Resting heart rate under 2.5mg (6±2weeks), 5mg (14±2weeks) and 10mg (26±2weeks) of Bisoprolol vs at baseline.

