8.4 Analysis Sets

- ***Screen Population***

The screening population will include all subjects who provide written informed consent and who undergo screening assessments, regardless of treatment status in the trial.

- ***Full Analysis Set (FAS)***

- Enrolled
- Presence of measurement at baseline and time point of interest

- ***Per Protocol (PP)***

The per protocol set of subjects is defined as a subset of the FAS analysis set who are compliant with the clinical trial protocol, and is characterized by criteria such as:

- The completion of a certain minimal exposure to the trial drug.
- The absence of any major clinical trial protocol violations.

Major protocol violation will be defined in the Statistical Analysis Plan (SAP).

The PP population will be identified before database lock and will be used to test the primary endpoint as sensitivity analysis..

- ***Safety***

The safety population will include all subjects who received at least one dose of trial treatment.

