8.5 Description of Statistical Analyses

8.5.1 General Considerations

Statistical analysis will be performed using CRF data obtained until database lock. The FAS population will be used primarily to present baseline characteristics and analyze efficacy data. Selected efficacy analyses will be repeated for the PP population.

If confidence intervals are to be calculated, 2-sided with significance level 0.05 is used, unless otherwise specified.

Continuous variables will be summarized using descriptive statistics, i.e., number of subject (N), mean, median, standard deviation (S.D.), 25th and 75th percentile (Q1-Q3), minimum and maximum. Counts of missing observation will be included in the denominator and presented as a separate category.

For all variables, the baseline value will be defined as the last measurement taken prior to the first administration of treatment drug.

The dropouts and missing data will not be imputed.

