8.5.2 Analysis of Primary Endpoints

Liner regression will be applied with change from baseline of HR as dependent variable and baseline HR and age as covariates at week 6, 14 and 26, respectively.

Furthermore, the mean value, standard deviation and 95% confidence interval (CI) will be calculated for the difference between HR at baseline and after week 6, 14 and 26 weeks treatment.

This analysis will be done both in FAS population and PP population.

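### The 95% CI half-widths in 8.1 (1.54 and 2.12 bpm) are not those of the planned FAS analysis (1.28 to 1.39 bpm) and appear to rest on undisclosed on-dose shares

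*Combined protocol and SAP*

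**What the plan says.** Section 8.1, repeated in the Synopsis under Statistical methods, assumes mean changes of -3.8 bpm at week 6 and -7.4 bpm at week 14. On spread it says: "The Standard Deviation is assumed to be 10bpm across time". From 236 subjects and 15% dropout it then gives the distance from the mean to the 95% limit for the "change from baseline of mean heart rate is 1.54 at week 6 and 2.12 at week 14". It introduces these figures with "Based on assumption above about treatment effect and up-titration status at different visit", but states no number or share of subjects at any dose. For the third primary time point it says only: "Due the limit evidence at week 26, there is no robust extrapolation".

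The primary endpoint in 8.3.1 is worded by dose and week together: "Resting heart rate under 2.5mg (6±2weeks), 5mg (14±2weeks) and 10mg (26±2weeks) of Bisoprolol vs at baseline".

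The analysis is not worded that way. In 8.4 the FAS requires enrolment and "Presence of measurement at baseline and time point of interest". In 8.5.2 the mean, SD and 95% CI "will be calculated for the difference between HR at baseline and after week 6, 14 and 26 weeks treatment", alongside a linear regression on baseline heart rate and age at each of those weeks. Neither section mentions the dose being taken. Section 8.5.1 sets two-sided 95% intervals and adds: "The dropouts and missing data will not be imputed".

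**The concern.** One SD and one dropout rate should give nearly the same half-width at every visit. Section 8.1 gives two that differ by a factor of 2.12/1.54 = 1.38, and both look too wide for 200 or more subjects.

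The half-width is the only design property stated for this single-arm pilot. There is no power calculation and no success threshold, so it is the whole justification for 236 subjects. If the reader cannot derive it, the sample size has no checkable basis.

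The larger issue is what the primary result will mean. Under 5.1.1, up-titration depends on the investigator's judgement and on tolerance of the previous dose. Subjects measured at week 14 and subjects taking 5 mg at week 14 are therefore different groups. If 8.1 was computed for the second and 8.5.2 analyses the first, the plan holds two versions of its primary estimate.

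**Working it through.** **Inputs.** N = 236, dropout 15% and SD 10 bpm at all visits (8.1). Two-sided 95% (8.5.1). All subjects with baseline and visit values, no dose restriction, no imputation (8.4, 8.5.1, 8.5.2). The assumed mean changes do not enter a half-width.

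**Step 1: try to reproduce 8.1 from its stated inputs.** Half-width = t(0.975, n-1) × 10/√n, with 1.96 in place of t for the normal version.

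| Subjects at the visit | normal | t |
|---|---|---|
| 236 (no loss) | 1.276 | 1.282 |
| 236 × 0.85 = 200.6 | 1.384 | 1.392 |

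The timing of dropout only moves the result within this range. If losses accrue evenly over 26 weeks (an assumption), the normal half-widths are 1.30, 1.33 and 1.38 bpm at weeks 6, 14 and 26. The stated 1.54 is 1.54/1.39 = 1.11 times the widest value, and 2.12 is 2.12/1.39 = 1.53 times it.

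**Step 2: try other conventions** (normal version, n = 236 to 200.6).

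| Convention | Half-width, bpm |
|---|---|
| One-sided 95% | 1.07 to 1.16 |
| 99% | 1.68 to 1.82 |
| Bonferroni over three visits | 1.56 to 1.69 |
| SD × √2 | 1.80 to 1.96 |
| 15% loss compounded once to seven times | 1.38, 1.50, 1.63, 1.77, 1.92, 2.08, 2.25 |

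None gives both figures.

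**Step 3: invert the formula at SD 10.** n = (1.96 × 10/h)², with the t version solved numerically.

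| | Week 6, h = 1.54 | Week 14, h = 2.12 |
|---|---|---|
| n, normal | 162.0 | 85.5 |
| n, t | 164.4 | 87.9 |
| Loss needed with no dose condition | 1 - 165/236 = 30.1% to 1 - 162/236 = 31.4% | 1 - 88/236 = 62.7% to 1 - 86/236 = 63.6% |
| Share of 200.6 completers (normal) | 81% | 43% |
| Share of 236 (normal) | 69% | 36% |

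Alternatively, with n held at 200.6, the SD would have to be 11.1 at week 6 and 15.3 at week 14, which contradicts a constant 10.

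**Step 4: which reading fits?** Dropout of 30% and 63% contradicts the 15% in 8.1. On-dose shares of about 81% and 43% of completers contradict nothing, and they match the mention of up-titration status. On that reading, declining to give a week 26 figure is coherent. For the FAS as written it is not, because the stated inputs give 1.28 to 1.39 bpm at week 26 too.

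**Step 5: week 26 on dose, for illustration only.** Section 3.1.3 cites target-dose shares of 26% and about two thirds from other beta-blocker studies. Applied to 200 evaluable subjects:

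- 0.26 × 200 = 52 subjects, half-width 2.8 bpm (t)
- 2/3 × 200 = 133 subjects, half-width 1.7 bpm (t)

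These are not predictions for this trial.

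**The case against.** Four points can be made for the plan.

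- **It never claimed FAS precision.** Section 8.1 names up-titration status as an input, and the objective (4.1), the endpoint (8.3.1) and the visit labels in 7.1 are all tied to dose. On this view only 8.4 and 8.5.2 are out of line. This stands as far as it goes: no calculation slip has been shown. But the shares are still missing, and the sections out of line are the ones that define the analysis. The PP set does not close the gap. Section 8.4 describes it by minimal exposure and absence of major violations, and leaves the definition of violations to the SAP. No such definition appears in the text supplied.

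- **The SD of 10 might be that of heart rate at a visit, not of its change.** The SD of change is then 10√(2(1 - r)), where r is the correlation between baseline and visit. An r of about 0.27 to 0.38 would give 1.54 with 236 to 200.6 subjects. However, 2.12 would need r of about -0.38 to -0.17, which is implausible for repeated heart rates in one person. One SD and one dropout rate also cannot explain a variance ratio of (2.12/1.54)² = 1.9 between visits. And the SD sentence follows directly on one about mean change.

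- **Week 26 was left out for a stated reason.** That is fair for an on-dose figure, and the shares from other studies deserve no weight beyond illustration. It does not apply to the FAS figure.

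- **The consequence is limited.** This is an exploratory pilot with no threshold, and the stated widths are wider than the FAS will need. That is right, and it is why this is a point to fix rather than a threat to the trial.

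**Conclusion.** The concern holds. For the primary analysis as written, the stated inputs give a half-width of 1.28 to 1.39 bpm at each of weeks 6, 14 and 26. The figures in 8.1 are 11% and 53% wider than the upper end, and they correspond to about 162–165 and 86–88 subjects rather than 200 to 236.

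This rests on reading the SD of 10 as that of the change, constant over visits including week 26, and on at most 15% loss. The range is for the unadjusted mean change. The regression on baseline heart rate and age should have a residual SD of 10 or less, so its interval would be about as wide or narrower.

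That the figures count on-dose subjects is the likely explanation but remains an inference. The fault is an undisclosed input and a population that differs from the one in 8.4 and 8.5.2. If on-dose is what the sponsor means, the 10 mg time point has no stated precision at all. It should be fixed. Confidence is high.

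**What to change.** 1. In 8.1 and the Synopsis, give the figure that belongs to the analysis as written. For example: with 236 subjects, up to 15% dropout and an SD of change of 10 bpm, the 95% CI half-width for the mean change in the FAS is about 1.4 bpm at each of weeks 6, 14 and 26.
2. If 1.54 and 2.12 are kept, label them as on-dose precision. State the sponsor's own assumed share on the scheduled dose at each visit with its source, giving week 26 as a share or a range. Define the on-dose set in 8.4 and its analysis in 8.5.2.
3. Before database lock, state which of the two analyses is primary, so that 8.1, 8.3.1, 8.4 and 8.5.2 agree.

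The cost is about two sentences in 8.1 and the Synopsis, plus a short definition in 8.4 and 8.5.2 if the on-dose figures stay. Enrolment, visits and data collection are unaffected.

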8.2 Randomization

Not Applicable.

8.3 Endpoints

8.3.1 Primary Endpoints

Resting heart rate under 2.5mg (6±2weeks), 5mg (14±2weeks) and 10mg (26±2weeks) of Bisoprolol vs at baseline.

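### The primary endpoint is defined by dose but analysed by week whatever the dose, and the precision in Section 8.1 does not belong to that analysis

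*Combined protocol and SAP*

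**What the plan says.** The primary objective (4.1) and the stated main purpose (5.2) concern heart-rate control under different doses. Section 8.3.1 follows them: "Resting heart rate under 2.5mg (6±2weeks), 5mg (14±2weeks) and 10mg (26±2weeks) of Bisoprolol vs at baseline".

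Section 8.5.2 specifies linear regression "with change from baseline of HR as dependent variable and baseline HR and age as covariates at week 6, 14 and 26, respectively". It adds that the "mean value, standard deviation and 95% confidence interval (CI) will be calculated for the difference between HR at baseline" and weeks 6, 14 and 26. Both are run in the full analysis set (FAS) and the per-protocol (PP) set. The FAS in 8.4 requires enrolment and "Presence of measurement at baseline and time point of interest". The PP set is described by example (minimal exposure, no major violations), and the definition of a major violation is left to the SAP.

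Under 5.1.1, each up-titration is judged by the investigator and requires that the previous dose was well tolerated. Intolerance may be a resting heart rate below 55 bpm, low blood pressure or an adverse event.

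Section 8.1 states "The Standard Deviation is assumed to be 10bpm across time". Then, "Based on assumption above about treatment effect and up-titration status at different visit" and "assuming 236 subjects under 15% dropout rate", it gives 95% half-widths of 1.54 bpm at week 6 and 2.12 bpm at week 14. It declines to extrapolate to week 26.

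**The concern.** A by-week mean and an on-dose mean are the same quantity only if the visit fixes the dose, and here it does not. A subject held at a lower dose who still has a week-14 reading meets the FAS definition and enters the week-14 mean, although the endpoint labels that mean as 5 mg. Whether a subject moves up depends partly on heart rate, which is the outcome itself. Section 3.1.3 says that recommended target doses are rarely reached and that heart-rate reduction was the main limit on up-titration, so the gap is a realistic possibility.

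An analyst working from 8.4 and 8.5.2 would use everyone measured at week 14. One working from 8.3.1 would use only those on 5 mg. Both could claim to follow the plan. If the all-subject mean is reported under the dose label, readers may take it as the effect under 5 mg or 10 mg. The two different half-widths in 8.1 suggest that the sample size was planned for something other than the analysis written in 8.5.2.

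**Working it through.** **Inputs.** From 8.1: SD of change 10 bpm at all times, 236 subjects, 15% dropout, half-widths 1.54 (week 6) and 2.12 (week 14). From 8.5.1: two-sided intervals at the 0.05 level. The assumed mean changes (-3.8 and -7.4 bpm) do not affect the half-width.

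**Step 1: try to reproduce the stated half-widths for the by-week mean in 8.5.2.**

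- Evaluable subjects: 236 × 0.85 = 200.6.
- Half-width = 1.96 × SD / √n = 1.96 × 10 / √200.6 = 1.38 bpm (1.39 with a t quantile).
- If no dropout has yet occurred: 1.96 × 10 / √236 = 1.28 bpm. The plan does not state when dropout occurs.

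With a constant SD and a single dropout rate, the result is the same at both weeks, so these inputs cannot give two values. Other conventions also fail:

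| Variant | Half-width (bpm) |
|---|---|
| n = 236/1.15 | 1.37 |
| One-sided 95% | 1.16 |
| 99% interval | 1.82 |
| Bonferroni over 2 / over 3 time points | 1.58 / 1.69 |
| SD × √2 | 1.96 |
| 15% dropout compounded over 2, 3, 4, 5, 6 steps | 1.50, 1.63, 1.77, 1.92, 2.08 |

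None gives 1.54 or 2.12.

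**Step 2: find what the stated half-widths imply.** Inverting, n = (1.96 × 10 / h)².

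| | Week 6 | Week 14 |
|---|---|---|
| Stated h (bpm) | 1.54 | 2.12 |
| Implied n (t-based) | 162.0 (164) | 85.5 (88) |
| Share of 200.6 | 81% | 43% |
| Share of 236 | 69% | 36% |
| Loss from 236 if attrition alone explained it | 31% | 64% |
| SD needed if n stayed at 200.6 | 11.1 | 15.3 |

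The losses are far above the stated 15%, and the SDs contradict a constant 10. A subset on the labelled dose, about 81% and 43% of evaluable subjects, fits the figures and the reference to up-titration status. The documents state neither those shares nor such a subset, so this is an inference.

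**Step 3: week 26.** On the by-week reading, with the same SD and the full 15% dropout, the half-width is again 1.38 bpm. On an on-dose reading it depends on a share that the plan does not give. Assumed shares of 43%, 30%, 20% and 10% of 200.6 give 2.11, 2.53, 3.09 and 4.38 bpm.

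**Limits.** These figures apply to the unadjusted mean change. The residual SD for the regression is not given. The number of subjects who stay on a lower dose rather than being withdrawn is also not given, so neither the size nor the direction of the difference between by-week and on-dose means can be calculated.

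**The case against.** The best defence is that dose and week are paired by design. Section 7.1 labels Visits 4, 6 and 8 as the 2.5, 5 and 10 mg measurements, so the dose in 8.3.1 can be read as the scheduled dose for the visit. The analysis in 8.5.2 would then match the endpoint, leaving only a labelling problem. But on that reading up-titration status has no role in the precision calculation, and 8.1 should show about 1.38 at both weeks. A correction is needed either way.

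Second, 8.1 names up-titration status as an input, so a calculation that omits it will naturally differ. This is fair: no arithmetic slip is shown. The defect is that the input is not quantified and has no counterpart in 8.4 or 8.5.2.

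Third, some subjects who cannot move up may leave the trial. The intolerance thresholds overlap the exclusion criteria, and 5.5.1 provides for stopping therapy when a relevant exclusion criterion arises. That would bring the two groups closer, but the step is discretionary and does not close the gap.

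Fourth, the deferred PP rules may contain a dose condition. They may, but 8.4 makes the PP analysis of the primary endpoint a sensitivity analysis; 8.5.1 uses the FAS primarily for efficacy.

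Finally, this is a single-arm exploratory pilot, and the stated widths are conservative if all measured subjects are intended. That stands and limits the harm. It does not settle who is included or how the result is labelled.

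**Conclusion.** The concern holds and should be fixed. The objective and primary endpoint are by dose, while the primary analysis and its main analysis set are by week with no dose condition. With the stated SD of 10 bpm, 236 subjects and 15% dropout, the written by-week mean has a half-width of 1.38 bpm at both weeks (1.28 if dropout has not yet occurred), against the stated 1.54 and 2.12. The stated precision therefore belongs to some other analysis. Restriction to subjects on the labelled dose is the natural explanation, but it is not stated. The consequence is an ambiguous primary quantity, not a demonstrated bias.

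**What to change.** 1. State in 8.3.1, 8.4 and 8.5.2 which quantity is primary: the by-week mean under the titration regimen, or the mean in subjects on the labelled dose at that visit. If the latter, note that this group is selected by tolerance and heart-rate response. Do not report an all-subject by-week mean as the effect under 5 mg or 10 mg.
2. Restate 8.1 to match. For the unadjusted by-week mean now written, give about 1.38 bpm at weeks 6 and 14, and at week 26 if the same SD and dropout are assumed. Otherwise keep 1.54 and 2.12 as the precision of an on-dose analysis, and state the assumed on-dose shares.
3. Show the achieved-dose distribution beside each primary mean. A dose-by-time mixed model is optional.

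The cost is wording in these four sections and in the places that repeat the endpoint or precision statement (synopsis and 5.1.1), plus one dose-by-visit table. It may need handling as a substantive amendment under 10.5. No new data are needed: use of study drug is recorded at every visit from Visit 2, and drug exposure is already listed in 8.3.4. The drawback for the sponsor is that a by-week mean can no longer be presented as a simple effect of 5 mg or 10 mg. None of this changes a dose or a titration rule.
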